**Hematology:**

WBC
Hemoglobin
Platelet Count

**Study Visit #4: Week 4 Reveal Visit (+/- 3 days)**

This visit will serve to review any adverse events, concomitant medications, and record dialysis treatment data from the baseline month of usual HD care. Subjects will be randomized to a treatment arm of Study A/B and will start study treatment on the next start of their short-interdialytic period (either Monday or Tuesday.) The Baseline Observation Period ends at this visit. Subjects should have completed at least 6 of their 12 scheduled dialysis treatments by this visit.

**\*Procedure for Missed Dialysis Treatments During Baseline Observation Period:**

At the end of the Baseline Observation Period, subjects who have missed more than half of their treatments (7 or more) during this time will "make up" treatments by extending the observation period for 1 or 2 weeks, beginning on the first Monday or Tuesday upon their return. The treatment intervention schedule will be adjusted accordingly.

### **Study A Intervention - Dialysate K/HCO3 Trial: Monthly Visits:**

Study treatment to be started on the 1st Monday/Tuesday following the Week 4 Reveal Visit. There will be 4 crossover groups and subjects will rotate monthly through all the treatment groups in a random blinded order. Prior to initiation of all HD sessions, subjects will receive POC testing via the Abbott i-STAT, which requires approximately 100uL of blood. This testing, along with their treatment arm assignment, will drive the dialysate prescription for that specific HD session (see figures/tables further below). The 4 cross-over groups are listed below:

- i. Potassium Removal Maximization strategy, 1 month (low dialysate K)
- ii. Potassium Gradient-Minimization Strategy, 1 month (high dialysate K)
- iii. Acidosis Avoidance, 1 month (low dialysate bicarbonate)
- iv. Alkalosis Avoidance, 1 month (high dialysate bicarbonate)

There will be a 1-week washout period between subsequent interventions and during this week, participants' dialysate prescription will be determined by their dialysis physician. Dialysis treatment records will be reviewed at least monthly and standard of care labs will be recorded at visits 5 through 8.

Subjects enrolled in the optional substudy will press the button on the REVEAL patient assistant device to automatically trigger their implanted REVEAL LINQ ILR to record an EKG tracing each time their blood drawn is drawn by the dialysis staff prior to dialysis for POC testing. Subjects will also record a full transmission upon returning home from dialysis with the Carelink Transmitter.

### **Study Visit #5: Study A Week 5 Visit (+/- 5 days)**

Visit to take place either at dialysis unit or by phone. Subject will be queried for Adverse Events and any changes in health or medications. Dialysis records will be reviewed for standard of care labs and hemodialysis treatment details. Subjects will begin their first treatment period and will receive the treatment intervention assigned for this period with each dialysis session (weeks 5-8.) Subjects who have missed more than half of the treatments (7 or more) during this period will "make up" treatments by extending the first treatment period for 1 or 2 weeks and continue receiving the first assigned intervention. The extension weeks will be referred to as Week 8-1 and Week 8-2 (not week 9 and 10) in order to maintain the schedule of events. The schedule of study visits will be adjusted accordingly. Week 9 will be a washout period.

### **Study Visit #6: Study A Week 10 Visit (+/- 5 days)**

Visit to take place either at dialysis unit or by phone. Subject will be queried for Adverse Events and any changes in health or medications. Dialysis records will be reviewed for standard of care labs and hemodialysis treatment details. Subjects will begin their second treatment period and will receive the treatment intervention assigned for this period at each dialysis session (weeks 10-13.) Subjects who miss more than half of the treatments (7 or more) during this period will "make up" treatments by extending this treatment period for 1 or 2 weeks and continue receiving the assigned intervention. The extension weeks will be referred to as Week 13-1 and Week 13-2. Week 14 will be a washout period.

### **Study Visit #7: Study A Week 15 Visit (+/- 5 days)**

Visit to take place either at dialysis unit or by phone. Subject will be queried for Adverse Events and any changes in health or medications. Dialysis records will be reviewed for standard of care labs and hemodialysis treatment details. Subjects will begin their third treatment period and will receive the treatment intervention assigned for this period at each dialysis session (weeks 15-18.) Subjects who miss more than half of the treatments (7 or more) during this period will "make up" treatments by extending this treatment period for 1 or 2 weeks and continue receiving the assigned intervention. The extension weeks will be referred to as Week 18-1 and Week 18-2. Week 19 will be a washout period.

**Study Visit #8: Study A Week 20 Visit (+/- 5 days)**

Visit to take place either at dialysis unit or by phone. Subject will be queried for Adverse Events and any changes in health or medications. Dialysis records will be reviewed for standard of care labs and hemodialysis treatment details. Subjects will begin their fourth and final treatment period for Study A and will receive the treatment intervention assigned for this period at each dialysis session (weeks 20- 23.) Subjects who miss more than half of the treatments (7 or more) during this period will "make up" treatments by extending this treatment period for 1 or 2 weeks and continue receiving the assigned intervention. The extension weeks will be referred to as Week 23-1 and Week 23-2.

**\*Procedures for Missing Consecutive Dialysis Treatments During Intervention Periods in Study A:**

Subjects who have missed less than 6 consecutive weeks, can also "make-up" treatments with a 2-week extension that will begin on the first Monday or Tuesday upon their return to the dialysis clinic. Subjects will receive their last assigned intervention during these make up treatments and the study schedule and dates of their remaining study visits will be adjusted accordingly.

In the event that a subject does not receive outpatient dialysis at his or her usual outpatient dialysis clinic for six consecutive weeks or more, the subject will be reassessed by the site investigator for suitability before continuing in the trial. If deemed appropriate to continue in the study, the rules as described above will be applied so that the subject receives at least 6 dialysis treatments of the assigned intervention.

Although all intervention periods will be scheduled to start on the 1st Monday or 1st Tuesday of a week, no special provision will be made to extend the intervention period if subjects miss their treatment on these days, provided they are able to complete at least 6 dialysis treatments of the assigned intervention. The intervention will simply start on the next scheduled dialysis treatment.

**Study B Intervention- Ultrafiltration Rate Trial: Biweekly Visits:** Study treatment to be started on the Monday/Tuesday following the Week 4 Reveal Visit. There will be 2 treatments and subjects will rotate back and forth weekly during an 8-week period in a random order. Dialysis unit records will be reviewed at least monthly and standard of care labs will be recorded at visits 5 and 8.

- i. **Restricted UFR;** UFR  $\leq$ 10 ml/kg/hr: 4 alternating weeks
- ii. **Standard of Care/ Unrestricted UFR;** UFR as needed: 4 alternating weeks

**Study Visit #5: Study B Week 5 Visit (+/- 5 days)**

Visit to take place either at dialysis unit or by phone. Subject will be queried for Adverse Events and any changes in health or medications and dialysis treatment records and standard of care labs will be reviewed. Subjects will receive their randomized first UFR based treatment assignment during each dialysis treatment during week 5. Treatment will then switch to the alternate treatment strategy during week 6 at each dialysis session during the week. At the beginning of week 7, treatment will once again alternate back to the first treatment assignment.

**Study Visit #6: Study B Week 7 Visit (+/- 5 days)** Visit to take place either at dialysis unit or by phone. Subject will be queried for Adverse Events and any changes in health or medications and dialysis treatment records will be reviewed. Treatment assignments will continue alternating weekly between the two treatment options during Week 8 (second assignment) and Week 9 (first assignment.)

**Study Visit #7: Study B Week 10 Visit (+/- 5 days)** Visit to take place either at dialysis unit or by phone. Subject will be queried for Adverse Events and any changes in health or medications and dialysis treatment records will be reviewed. Treatment assignments will continue alternating weekly between the two treatment options during Week 10 (second assignment) and Week 11 (first assignment.)

**Study Visit #8: Study B Week 12 Visit (+/- 5 days)**

Visit to take place either at dialysis unit or by phone. Subject will be queried for Adverse Events and any changes in health or medications and dialysis treatment records and standard of care labs will be reviewed. Treatment assignment will alternate for the last time and subjects will receive the second assignment during this final intervention treatment (week 12.)

**\*Procedures for Missed Dialysis Treatments for UFR-based interventions in Study B:**

Subjects in Study B will cross-over between two different, week-long UFR-based interventions, alternating interventions each week for a total of 8 weeks. During this 8-week period, subjects will be scheduled for a total of 24 dialysis treatments at their dialysis clinic; 12 treatments of each of the two UFR-based interventions.

At the end of the 8-week treatment period, subjects who have missed more than half of the treatments (7 or more) for one or both of the two treatment interventions will have the opportunity to "make up" treatments by extending the treatment period for two to four more weeks in order to meet the minimum requirement of 6 treatments received within each treatment intervention.

This "make-up" treatment extension will be scheduled to start on the next Monday or Tuesday following the end of the 8- week treatment period (week 12) and treatment assignment for the first extension week must continue the alternating pattern to avoid a subject receiving the same treatment for two consecutive weeks.

For subjects who have missed less than 6 consecutive weeks, the extension will begin on the first Monday or Tuesday upon their return to the dialysis clinic. In the event a subject does not receive outpatient dialysis at his or her usual outpatient dialysis clinic for six consecutive weeks or more, the subject will be reassessed by the site investigator for suitability before continuing in the trial. If deemed appropriate to continue in the study, the rules as described above will be applied so that the subject receives at least 6 dialysis treatments for both of the assigned interventions.

**Study Visit #9: End of Treatment Visit**

Upon completion of either Study A or Study B, subjects will be screened and offered the opportunity to consent to participate in the other study. Subjects will be queried for adverse events and dialysis treatment records will be reviewed. If subjects elect to participate in both studies consecutively, then they will not need to redo the Week 1 Reveal insertion follow-up visits, since they will have already received a device. For subjects enrolling in both studies, a 1-week washout period is required (receive SOC hemodialysis treatment) and will then begin another 1-month of baseline monitoring prior to starting the intervention for the second study.

Once a subject has completed Study A and Study B, or a subject is no longer interested or eligible to participate in the second study, he or she will be given the option to come back to New York University Langone Medical Center for device removal. Subjects who choose to keep the device implanted after the last treatment will be followed for adverse events and concomitant medications for one week after this visit. Subjects who choose to have the device removed, will have two more study visits, one to remove the device and another to follow up on the removal procedure.

**Study Visit #10: Reveal LINQ Explanation Visit**

Following completion of Study A or Study B, subjects will be given the option to come back to the local site for device explanation. Due to the COVID-19 safety precautions, subjects may be provided with a COVID-19 nasal swab test as part of this visit. Subjects will be queried for adverse events, concomitant medications, and Reveal devices will be removed.

If coagulation labs are not clinically available within relevant timeframe (72 hours), then these will also be drawn at this visit. Platelet count must be available within 30 days of the procedure or it will be drawn at this visit. Coagulation parameters and platelet count (as needed) may be drawn up to 72 hours prior to the Reveal LINQ visit to ensure that they are available at the time of the procedure. If the subject is not taking an anticoagulant medication, the coagulation parameters and platelet count may be drawn up to 96 hours prior to the procedure. Concomitant medications will be recorded from this visit until one week after the last study related treatment. As needed for scheduling purposes the procedures needed to complete this visit may take place on more than 1 calendar day.

#### **Study Visit #11: Explant Follow Up Visit**

Following explanation, there will be a 1-week wound check visit either at the local site or at the dialysis clinic. Collection of adverse events and concomitant medications will conclude at this visit.

## **VI. Biostatistical Analysis**

Given an overarching aim to assess definitive trial feasibility, analyses will be considered exploratory and conservatively interpreted but no adjustment will be made for multiple comparisons.

**Trial Endpoints and Overview of Specific Aims:** The long-term goals are to conduct well-powered trials testing the effect of POC testing-guided management of dialysate potassium and bicarbonate or limitation of maximum UF rate on clinically significant arrhythmia (CSA) and hard cardiovascular events. The specific goals of Studies A/B in accordance with the R34 funding mechanism isto provide the key feasibility and effect-size data necessary to plan definitive, subsequent multi-center trials. Towards this end, data on:

- Aim 1: Adherence with Proposed Interventions
- Aim 2: Recruitment Feasibility
- Aim 3: Effect Estimates

**Adherence with Proposed Interventions (Aim 1)**— In routine practice, the dialysis prescription is adjusted by the physician only once per month in response to monthly laboratory results. Utilizing POC testing and daily adjustment of the dialysate prescription deviates from this standard considerably. Similarly, while a post-dialysis target weight is prescribed by dialysis providers, in routine practice, patients and nurses have daily discretion regarding UF rate. In short, protocolizing the interventions represent a significant change from standard of care that will require active engagement of both patients and HD-unit staff. Estimating the extent of protocol deviation and the safety of proposed interventions in this environment is critical to large-scale implementation of the proposed trials as biologic efficacy is immaterial if interventions cannot be scaled-up.

**Adherence Endpoints**—Adherence will be assessed for each of the 4 dialysate interventions (K removal minimization vs. maximization, acidosis vs. alkalosis avoidance) as the % of sessions in which POC testing is completed and the dialysate is adjusted according to the algorithm. For the UF trial, it will be assessed as the % of sessions in which the mandated UF rate is delivered. We hypothesize that 90% adherence is achievable. HD staff will be anonymously surveyed once 3 subjects have completed 1 month of each trial and once 6 patients have completed each trial. A questionnaire will identify the impact of time constraints, patient refusal, algorithm complexity, inadequate training on POC devices, clinical concerns, or other factors on protocol adherence. Face-to-face review with HD staff will facilitate identification of other barriers. Where addressable factors are identified, they will be corrected for remainder of the trials. Since the overall goal is to assess implementation feasibility, secondary analyses will compare pre- and post-correction adherence in addition to estimating overall adherence. This adaptive plan will facilitate identification of best practices and ensures that estimates represent the feasibility of subsequent protocols to be implemented after incorporating lessons learned in the pilot experience.

**Secondary Feasibility Measures**—POC electrolyte measurements will be compared with usual care monthly labs to assess accuracy of POC testing. An additional metric that will be used to determine the impact of POC testing on trial design will be the percent of sessions in which the POC-guided dialysate prescription differs from a hypothetical prescription in which the choice of dialysate is based solely on the once-monthly lab.

**Safety Endpoints**—The primary safety endpoint will include the incidence of all serious adverse events and intervention-specific complications: a) Potassium Intervention—severe K abnormalities ( $K \geq 6.5$  or  $\leq 3.0$  mEq/L), or unscheduled HD or hospitalization for hyper/hypokalemia in the absence of a missed treatment; b) Bicarbonate Intervention—severe  $HCO_3$  abnormalities ( $HCO_3 < 20$  or  $> 32$  mEq/L) or unscheduled HD or hospitalization for acid base abnormalities in the absence of a missed treatment; c) Ultrafiltration Intervention—Unscheduled HD or hospitalization for volume overload. Secondary safety endpoints include the occurrence of CSAs requiring further management, all-cause mortality, cardiovascular mortality, and hospitalization.

**Recruitment Feasibility (Aim 2)**—Recruitment feasibility will be analyzed by testing whether an overall recruitment rate of 1 patient/month is achieved in each trial (1-sample test). This is a critical metric, as a large-scale trial cannot be feasibly completed in a practical number of centers if between 0.5-1 patient/month cannot be enrolled. This rate represents a minimum criterion for feasibility.

The percent of screened patients enrolled will be calculated as a secondary feasibility measure to assess the size of the necessary screening pool. Reasons for non-enrollment (vis-a-vis inclusion and exclusion criteria and patient and physician preferences) will be assessed to determine the potential for protocol modification to improve recruitment. Subject retention will be calculated as the percentage of enrolled patients completing the trial. Retention rates of 90% will be considered the benchmark for feasibility.

**Effect Estimates (Aim 3)**—Estimating the mean and standard deviation (SD) of the change in duration of clinically significant arrhythmia (CSA) per month is critical for power and sample size calculation and planning definitive studies. The total monthly duration of CSA (in minutes) will be utilized as the primary efficacy endpoint in comparing each pair of interventions (K removal maximization vs. minimization, acidosis vs. alkalosis avoidance, aggressive vs. conservative UF). In the event of incomplete follow-up, CSA duration will be indexed to follow-up time. CSA will be defined on the basis of arrhythmias likely to lead to SCA or serious morbidity and mortality and will include AF, asystole  $\geq 3$  seconds, bradycardia  $\leq 40$  beats per minute lasting  $\geq 6$  seconds, and sustained VT  $\geq 130$  beats per minute lasting  $\geq 30$  seconds. CSA's will be adjudicated by study electrophysiologists.. Currently, no data exists on the expected impact of the interventions on CSA duration, but given a mean duration of CSA in MiD of  $356 \pm 1765$  minutes, a sample size of 20 subjects provides 80% power for detection of change in CSA duration of 140 minutes/month given within-subject correlation of 0.9, 370 minutes for within-subject correlation of 0.7, and 470 minutes if within-subject correlation is 0.5.

**Statistics and Analysis**—A balanced, uniform crossover design will be used with randomization stratified by site in blocks of 4.

**Adherence** will be estimated as % (95% CI) of sessions without protocol deviation. Comparison of adherence percentage pre- vs. post-interim analysis of adherence will be made using linear regression with time period as an independent variable. Exploratory analyses will assess association of adherence with site, dialysis shift (1st-3rd), and day (Monday/Wednesday/Friday or Tuesday/Thursday/Saturday).

**Safety** will be assessed by calculating the incidence rate (complications per unit follow-up time) for serious adverse events and intervention-specific complications. Comparisons of incidence rate between interventions will utilize Poisson regression adjusted for randomization scheme and site. Exploratory analyses will assess age, sex, race, mean intra-dialytic weight gain, potassium concentration and HCO3 concentration in month prior to randomization on the incidence of adverse events. Given the pilot nature of the trials and major goal of informing feasibility estimates for definitive trials, P<0.05 will be considered significant in all safety analyses. No adjustments will be made for multiple comparisons given the pilot nature of the studies.

**Efficacy** estimates for Aim 3 will utilize the mean duration of CSA as the primary outcome. In the event of incomplete follow-up, this will be indexed to duration of follow-up time (e.g. minutes per day). Change in CSA duration between interventions will be analyzed using mixed effects linear regression with terms for treatment, research site, period, sequence, and random effects for subjects. Primary outcomes for the dialysate trial will compare CSA during potassium maximization vs. minimization, and acidosis vs. alkalosis avoidance. For the UF trial, aggressive vs. conservative UF will be compared. Physiologically, the washout period of 1-week in the dialysate trial and 1 weekend in the UF trial is sufficient to avoid the possibility of carryover effects. Potential for sequence effects is minimized by a design with uniform sequences (all treatments appear once within each sequence). Potential for carryover and randomization sequence effects will be analyzed by including terms for sequence and their interaction with treatment in the models.

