## II. Specific Aims

Overview of Trial Design—The overall goal for these trials is to provide the data necessary for the design of definitive clinical trials. Specifically, we aim to test recruitment feasibility, the feasibility of POC electrolyte measurement and POC-directed management of the dialysis prescription, and to provide preliminary estimates of effect size with manipulation of UF rate, dialysate K, and dialysate HCO3. We will perform two related, randomized cross-over trials; Study A- dialysate interventions trial, consisting of 2 dialysate potassium interventions and 2 dialysate bicarbonate interventions (4 total cross-over interventions); and Study B-ultrafiltration rate intervention trial, consisting of 2 separate ultrafiltration rate strategies.

The central hypothesis underlying Study A and Study B is that the risk of clinically significant arrhythmias in HD patients can be reduced by altering components of the dialysis prescription.

**Aim 1—To test the feasibility and safety of POC-guided dialysate prescription adjustment and the feasibility of limiting UF rate in HD patients.** The current studies will pilot our educational strategies and the dialysate potassium, dialysate bicarbonate and UF intervention strategies to test their feasibility in a multi-center setting. They will test the hypothesis that  $\geq 80\%$  adherence with proposed interventions is feasible, and that the safety need for unscheduled dialysis or severe abnormalities in potassium and bicarbonate will be minimal.

**Aim 2—To assess recruitment feasibility and retention rate for trials combining ILR insertion to monitor arrhythmia and interventions using POC-guided dialysis prescription or UF rate manipulation.** Screen failures and retention rates will be captured and analyzed. Whether recruitment rates  $\geq 1$  patient per month and retention rate  $> 90\%$  are achievable in each study will be tested.

**Aim 3—To refine effect estimates of the change in monthly CSA duration during Study A (dialysate potassium intervention to maximize vs. minimize intradialytic potassium removal) and Study B (aggressive vs. conservative ultrafiltration rate).** Refining estimates of change in CSA with each pair of interventions will provide key information necessary for design of definitive trials. Whether CSA decreases with minimization of potassium removal, alkalosis limitation and UF rate minimization will be tested.

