**Potassium (K) Intervention**—This intervention will test whether minimizing intradialytic fall in serum K **Dialysate Potassium Intervention Algorithm** by using higher K dialysates to minimize serum-dialysate K gradients reduces the incidence of CSAs compared to an approach prioritizing lower K dialysate to reduce the incidence of hyperkalemia. This will be achieved by utilizing an algorithm which couples POC-testing with the choice of one of two dialysate K concentrates (2 or 3 mEq/L potassium, **Table [left]**) that are widely available in dialysis clinics. Although there is potential equipoise regarding use of very low K dialysates (1 mEq/L) in hyperkalemic patients, 1K dialysate is either restricted or not available in the majority of US outpatient HD units.

POC Serum K (mEq/L)	Dialysate K (mEq/L)	Gradient (mEq/L)
K removal maximization Strategy		
<4	3	0
4-5.0	3	1-2
5.1-6.3	3	2.1-3.3
$\geq 6.4$	2	$\geq 4.4$
Gradient-Minimization Strategy		
<4	3	0-1
4-5k	2	2-3
5.1-6.3	2	3.1-4.3
$\geq 6.4$	2	$\geq 4.4$

substudy. Participants in the substudy will be asked to press the button on the REVEAL patient assistant device to automatically trigger their implanted REVEAL LINQ ILR to record an EKG tracing each time their blood drawn is drawn by the dialysis staff prior to dialysis for POC testing. Patients will also be asked to perform a full transmission upon returning home from dialysis to assure an adequate length of EKG tracing is obtained before and after the patient assistant button is pressed at dialysis.

**Bicarbonate (HCO3) Intervention**—The bicarbonate intervention is designed to compare an algorithm designed to avoid acidosis (by use of lower dialysate HCO3) with one that avoids alkalosis (by use of higher dialysate HCO3). As shown in the **Table (right)**,

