Study procedures ensure testing of electrolytes at each session (3x/week) in contrast to a frequency of as little as 1x/month in routine practice. Severe electrolyte abnormalities will thus be recognized earlier with study patients than in routine practice. Similarly, POC testing will ensure that the dialysis prescription will be adjusted according to the ambient potassium or bicarbonate at that dialysis session. In routine practice, follow-up testing at outpatient dialysis units typically has a turn-around time of hours (stat testing) or days (routine lab draws) which makes appropriate adjustment of the dialysis prescription unfeasible. Thus, study procedures may actually lower the risk of severe electrolyte abnormalities or risk of complications from those abnormalities. However, significant inaccuracy in the point of care testing results could modify the associated risks.

To further mitigate risk, patients with severe abnormalities in potassium ( $K>6.5$  or  $<3.0$ ) or bicarbonate ( $<20$  or  $>32$ ) will temporarily come off therapy and be treated off-protocol at the discretion of their clinician.

**Study B UF algorithms** are designed to either limit UF rates to  $\leq 10$  mL/kg/hour or to allow UF rates  $\geq 13$  mL/kg/hour. As discussed in the research summary, there is significant equipoise regarding the risk/benefit ratio of either strategy, as the use of high UF rates minimizes the risk of volume overload at the expense of rapid fluid shifts, whereas limiting UF rate minimizes the risk of rapid fluid shifts at the expense of increasing the risk of volume overload. Both strategies are routinely employed in clinical care. Thus, it is again unclear whether research-related risks are materially different than those in routine practice. As described in the Research Plan, subjects will cross over weekly between the unlimited and restricted UF treatments, thereby allowing removal of excess fluid accumulated during the restrictive week during the subsequent, unlimited week. This will limit any excessive fluid gains to a maximum of a few liters over the course of the restricted UF week thereby limiting the possibility of volume-related complications in the event patients fail to self-regulate intake of salt and water. Safety, will be further ensured because patients who show signs of significant volume overload will have the

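### For potassium, the overall adherence percentage says little about whether staff act on a POC result that calls for the other bath, because each strategy has one standing bath and one exception

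*Combined protocol and SAP*

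**What the plan says.** Aim 1 in section II is "To test the feasibility and safety of POC-guided dialysate prescription adjustment", together with the feasibility of limiting the UF rate. Its hypothesis is that at least 80% "adherence with proposed interventions is feasible". Section VI (Adherence Endpoints) gives a different target: "We hypothesize that 90% adherence is achievable". There, adherence is assessed for each of the four dialysate interventions "as the % of sessions in which POC testing is completed and the dialysate is adjusted according to the algorithm". Under Statistics and Analysis it is estimated as a percentage with a 95% CI "of sessions without protocol deviation".

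The potassium algorithm in section V "couples POC-testing with the choice of one of two dialysate K concentrates". As printed, the first block gives 3 mEq/L in every row below K 6.4 and 2 mEq/L at 6.4 or above. The second gives 2 mEq/L in every row from K 4 upward and 3 mEq/L below 4. I call them the 3-mEq/L and 2-mEq/L blocks after their standing bath. The strategy labels printed in the table run opposite to the descriptions in the Study Summary and in the Study A text of section V, and these places must be reconciled. The arithmetic below does not depend on which label is meant.

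Section VII, item iii, adds that patients with K above 6.5 or below 3.0 "will temporarily come off therapy and be treated off-protocol at the discretion of their clinician".

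**The concern.** Section VI describes per-session adjustment of the dialysate as a considerable departure from monthly prescribing, and asks whether it can be scaled up. To answer that for potassium, the measure should respond to whether staff change the bath when the POC value calls for it. As defined, a session with the test done and the standing bath running counts as adherent whenever K lies outside the exception zone, whether or not anyone used the result. The off-protocol rule narrows that zone further: the exceptions that stay on protocol are K 6.4-6.5 in the 3-mEq/L block and K 3.0-3.9 in the 2-mEq/L block.

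If exceptions are rare, a high percentage is compatible with a fixed order plus an unused test. A definitive POC-guided trial could then be planned on a figure that carries little information about the step in question.

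**Working it through.** The plan derives no adherence figure. The 80% and 90% values are hypotheses with no calculation attached, so there is nothing to reproduce. The check asks what a unit would score if it sets the standing bath at the start of each period, runs the POC test and never changes the bath.

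**Inputs from the documents.** Switch points 6.4 and 4 (section V table). 20 patients per trial and 12 scheduled sessions per period, so 20 × 12 = 240 sessions per strategy (section V). The only average pre-dialysis K is 5.0 mEq/L (section I), and it describes patients with cardiac arrest on low-K dialysate, not this population. No SD is given.

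**Assumptions.** Session K is normal with mean m from 4.4 to 5.4 and SD s from 0.5 to 1.0. POC completion c is 90-100%.

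**Formulas.** Expected adherence under a standing bath:
- 3-mEq/L block: c × Φ((6.4 − m)/s)
- 2-mEq/L block: c × [1 − Φ((4 − m)/s)]

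**At m = 5.0, s = 0.8.** Φ(1.75) = 96.0% and 1 − Φ(−1.25) = 89.4%. With c = 95% these become 91.2% and 85.0%; with c = 90%, 86.4% and 80.5%.

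**Across the range, c = 100%.** The 3-mEq/L block scores 84.1-100% throughout. At its worst corner (m = 5.4, s = 1.0), 95% completion gives 0.95 × 84.1% = 79.9%. The 2-mEq/L block scores 84.1-97.7% at m = 5.0, 77.3% at m = 4.6 with s = 0.8, and 65.5-78.8% at m = 4.4.

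**Mean K at which the 2-mEq/L block reaches 80%.** With c = 100% and s = 0.8: 4 + 0.8 × 0.842 = 4.67. With c = 95% the bath must match in 0.80/0.95 = 84.2% of sessions (normal quantile 1.003): 4 + 1.003s = 4.70, 4.80 and 4.90 for s = 0.7, 0.8 and 0.9. For 90% adherence with c = 100% and s = 0.8, the mean must be at least 5.03.

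**Chance that a simulated trial of 20 × 12 sessions scores at least 80%.** K is rounded to 0.1, c = 95%, and between/within-patient SDs are 0.5/0.5 and 0.6/0.6 (total √0.50 = 0.71 and √0.72 = 0.85).

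| Mean K | 3-mEq/L block | 2-mEq/L block |
|---|---|---|
| 4.6 | about 100% | 14-37% |
| 4.8 | about 100% | about 54-85% |
| 5.0 | over 99% | 89-99% |
| 5.2 | about 95-100% | 99-100% |

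At mean 5.0, the chance of at least 90% is about 52-87% and 9-37%.

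**Sessions that exercise the switch (m = 5.0, s = 0.8).** 2-mEq/L block: 240 × 10.6% = 25. 3-mEq/L block: 240 × 4.0% = 10, of which about 2 lie in 6.4-6.5 and stay on protocol. The Wald 95% half-width, ignoring clustering and with true adherence of 80% or 50%, is 16-20 points on 25 sessions and 25-31 points on 10. Two sessions support no estimate.

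**Bicarbonate.** That algorithm has several bands with different concentrations. With assumed mean 22-25 and SD 2.5-3, and one band inferred from its printed gradient, a single fixed concentration would match only about 40-68% of sessions.

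**The case against.** A reader might infer that staff who do nothing would pass, that they would often reach 90%, and that POC-guided adjustment would be declared feasible without being tested. The documents do not support that.

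- Setting the assigned standing bath is a real protocol action, because usual care applies at baseline and in washout. At m = 5.0, s = 0.8, a unit that leaves 2 mEq/L running in the 3-mEq/L block scores about 4%, and the reverse about 11%. The existing measure catches such units.
- POC completion is half of the definition and is tested. The bicarbonate strategies need adjustment at several levels and are assessed separately.
- The K distribution is assumed. At mean 4.6 the 2-mEq/L block usually falls short of 80%, and at mean 5.0 it seldom reaches 90%.
- Taking a patient off protocol at K above 6.5 is itself acting on the result. The 30-day eligibility limits on K do not truncate later sessions.
- Section VI already plans to report how often the POC-guided prescription differs from one based on the monthly lab alone. It also calls the analyses exploratory, and no go/no-go rule is tied to 80% or 90%.

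All of this stands and limits the claim. It does not remove it. The planned comparison shows how often POC would alter the prescription, not whether staff delivered the change when it was due.

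The objection also rules out one remedy. Judging Aim 1 on switch sessions alone would give 100% to a unit that leaves the opposite bath in place throughout, although its overall adherence is only about 4-11%.

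**Conclusion.** The point holds in a limited form. Each potassium strategy has one switch point, and the adherence score does not separate the sessions that call for the other bath; both follow from the documents alone. The size depends on an assumed K distribution. With SD 0.7-0.9, a standing bath plus an unused test would probably pass 80% in the 3-mEq/L block over the range of means considered, and in the 2-mEq/L block if mean pre-dialysis K is about 4.8-5.0 or higher. Reaching 90% is plausible in the first block and uncommon in the second at mean 5.0.

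The overall percentage is valid evidence on POC completion and on delivery of the assigned bath. It is weak evidence that staff act on a POC result calling for a different potassium bath. The remedy is a reporting improvement that also limits what Aim 1 may conclude for potassium.

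**What to change.** In section VI (Adherence Endpoints), keep the overall percentage as the main adherence figure. For each potassium strategy, report beside it:

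- (a) the percentage of sessions with the POC test completed;
- (b) the number of sessions in which the algorithm calls for a bath other than the standing one, with the proportion given the correct bath and a patient-clustered 95% CI.

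State how sessions taken off protocol under section VII, item iii, are counted in the overall figure and in (b). The choice matters: at m = 5.0, s = 0.8, c = 95%, limiting the 3-mEq/L block to K 3.0-6.5 moves the standing-bath score from 91.2% to 0.95 × 99.0% = 94.1%.

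Claim feasibility of POC-guided potassium adjustment only if both the overall figure and (b) support it. If (b) rests on too few sessions, limit the conclusion to POC completion and delivery of the assigned bath. Reconcile the strategy labels in the section V table with the Study Summary and the Study A text, and the 80% and 90% benchmarks with each other.

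The cost is analysis wording only, since scoring adherence already requires the POC value and the delivered bath. The drawback is that (b) rests on few sessions, roughly 2-25 of 240 per strategy at an assumed mean K of 5.0, so its interval will be wide.
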